## Brief Summary

The primary purpose of this study is to determine a safe and tolerable dose of LY3885125 in participants with dyslipidemia (Part A) and in participants with NAFLD and elevated ALT (Part B).

In Part A, the approximate total duration of study participation for each participant may be up to CCI days (CC weeks), across the following study intervals:

- Screening, approximately 28 days.
- Participants will be admitted to the site on Day -1 for an inpatient treatment period of approximately CC days, during which participants will receive a single dose of LY3885125 or placebo on Day 1. The single doses planned to be administered in Part A are as follows: CCI. If more than CC mL of solution is required to deliver a dose, then it will be split into multiple injections, each with a maximum volume of CC mL.
- Participants will then attend follow-up visits as outpatients for a minimum of 25 weeks as outlined in the schedule of activities.
- If discontinuation criteria are not met as outlined in the schedule of activities, participants will continue visits for up to a total of CC weeks, as needed, including during the Monitoring Extension, unless discontinuation criteria are met.
- Each participant in Part A will be followed until the plasma concentration of CCI has returned to at least CC% of the baseline level after administration of the single dose.

In Part B, the approximate total duration of study participation for each participant may be up to CCI days (CC weeks), across the following study intervals:

- Screening, approximately 28 days.
- Participants will be admitted to the site on Day -1 for the first inpatient treatment period of approximately 2 days, during which they will receive the first dose of LY3885125 or placebo (Day 1).
- Participants will attend the first series of follow-up visits as outpatients every other week post first dose as outlined in the schedule of activities.
- Participants will be readmitted to the site on CCI for a second inpatient treatment period of approximately 2 days, during which they will receive the second dose of LY3885125 or placebo (CCI).
- Participants will then attend a second series of follow-up visits as outpatients for a minimum of CC weeks post-second dose as outlined in the schedule of activities.

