Abbreviations: AE = adverse event; ApoB = apolipoprotein B; BP = blood pressure; COVID-19 = Coronavirus disease 2019; CRF = case report form; CRU = clinical research unit; D = day; ECG = electrocardiogram; ET = early termination; h = hour(s); FSH = follicle-stimulating hormone; HCV = hepatitis C virus; HDL-C = high-density lipoprotein cholesterol; I/E = inclusion/exclusion; ISR = injection-site reaction; LDL-C = low-density lipoprotein cholesterol; CCI min = minutes; P = predose; PCSK9 = proprotein convertase subtilisin/kexin type 9; PCR = polymerase chain reaction; PD = pharmacodynamics; PE = physical examination; PK = pharmacokinetics; PR = pulse rate; Q2W = once every 2 weeks; PUC = preparative ultracentrifugation; Q4W = once every 4 weeks; RR = respiration rate; SC = subcutaneous; TEAE = treatment-emergent AE; TG = triglyceride; VAS = visual analog score; VLDL-C = very low-density lipoprotein cholesterol.

- a All follow-up visits should take place in the morning after an overnight fast of at a minimum **CCI** hours. Water is permitted *ad libitum* during the fasting period.
- b After Day **CCI**, once any treatment related AEs are resolved and PCSK9 levels return to at least **CCI**% of baseline, the Monitoring Extension visits may be discontinued. The final visit of a participant who completes the study will be the first scheduled Monitoring Extension visit after they report no ongoing AEs, and after PCSK9 levels have returned to at least 80% of baseline in a blood sample collected at one of the preceding visits. At the participant's final visit, they will receive the assessments performed at ET, except for the collection of a blood sample for PCSK9 assessment.
- c Outpatient follow-up visits on Days **CCI** will be conducted through a remote telehealth visit assessing AE/concomitant medications.
- d On Day -1 prior to randomization review AEs, concomitant medications, and compliance to Inclusion/Exclusion criteria.
- e Discharge from CRU after all assessments have been completed.
- f All doses of study intervention will be administered SC in the morning after an overnight fast of approximately 8 hours duration.
- g Complete physical examination performed at Screening, ET and last visit., and symptom-directed examinations at all other visits.
- h Body weight is measured at any time before breakfast.

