### 4.3.4. Part B Dose

The dose of LY3885125 for Cohort 7 in Part B will not exceed what has already been dosed in Part A. The primary criteria for selection of dose for the first dose level in Part B will be safety and tolerability data from Part A. Additionally, changes in biomarkers of drug pharmacology in Part A may guide the dose selection. The protocol will be amended prior to initiation of Part B to define the dose and dosing frequency.

Although the predicted plasma half-life ( $t_{1/2}$ ) of LY3885125 is relatively short, the maximum effect is expected to be reached after [REDACTED] or more weeks and may take [REDACTED] months or longer to return to baseline levels after a single dose. The suitability of the proposed dosing interval of [REDACTED] days between the two doses to be administered in Part B will be informed by the rate of return of PCSK9 plasma concentrations in Part A study participants.

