### 5.3 Conventions

All data listings, summaries, figures, and statistical analyses will be generated using SAS version 9.4 or higher.

Part A summaries will be presented by treatment group. Treatment group labels for Part A TFLs will be displayed as follows, with the addition of “Part A Overall (N=XX)”, when appropriate:

QMD Ref: Worldwide-TMP-ST-054-1.0_Effective: 12Aug2022	Governing QMD: Worldwide-SOP-ST-026
Confidentiality Statement This document is the property of Worldwide Clinical Trials Inc. and may not be duplicated, copied, altered or removed from company without prior approval from Worldwide Quality Assurance or in compliance with Worldwide Standard Operating Procedures.	

Worldwide Clinical Trials Controlled Quality Management Document		
 WORLDWIDE CLINICAL TRIALS	Sponsor:	Eli Lilly and Company
	Protocol Number:	J4N-MC-YFAA
STATISTICAL ANALYSIS PLAN		

LY3885125 CCI (N=XX)	LY3885125 CCI (N=XX)	LY3885125 CCI (N=XX)	LY3885125 CCI (N=XX)	LY3885125 CCI (N=XX)	Pooled LY3885125 (N=XX)	Pooled Placebo (N=XX)
-----------------------------------	-----------------------------------	-----------------------------------	-----------------------------------	-----------------------------------	-------------------------------	-----------------------------

Part A listings will be sorted in the following order: treatment group, participant, parameter, and visit unless otherwise stated. All data will be listed, participants who were not randomized will be displayed after the randomized treatment groups/ arms.

Continuous variables will be summarized by the number of non-missing observations, mean, median, standard deviation, and minimum and maximum.

Categorical variables will be summarized by presenting the frequency and percent. Percentages will be based on the number of participants in the column header unless otherwise specified in the footnote. For each variable, all categories will be shown. Zero frequencies (but not the percent) within a category will be presented.

Means, medians and percentiles will be displayed to one more decimal place than the data, dispersion statistics (e.g., standard deviation) will have two more decimal places, and the minimum and maximum will be displayed to the same number of decimal places as reported in the raw data. Percentages will be displayed with one decimal place.

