### 5.11.1 Adverse Events

Treatment emergent adverse events (TEAE) are reported according to protocol as any AE that has an onset on or after the dose of study drug or any pre-existing condition that has worsened on or after the first dose of study drug. The following TEAE flag will be applied to distinguish AEs from TEAEs:

- Any AE that has a start date and time on or after the first dose of study drug

A treatment-related AE is defined as an AE with a causality of “Possibly Related”, “Probably Related”, or “Related” to LY3885125. If an AE has missing relationship it is assumed to be related to the study drug for analysis purposes.

Maximum severity (Severe) will be assumed for an AE with missing severity.

Events that occur after the last follow-up visit or early termination visit will only be included in any TFLs if they are “Possibly Related”, “Probably Related”, or “Related” to LY3885125.

The following tables will be presented for AEs incidence and/or number of events will be reported as appropriate, by treatment group and overall:

- Overall summary of TEAEs
- TEAEs by system organ class and preferred term
- Treatment related TEAE by system organ class and preferred term
- Serious TEAE by system organ class and preferred term
- TEAE by system organ class, preferred term and maximum severity
- TEAE by system organ class, preferred term and relationship
- TEAEs leading to early withdrawal by system organ class and preferred term
- Listing of Serious TEAEs (presented in the Table section of the appendices).
- Listing of Deaths (presented in the Table section of the appendices).

Adverse event incidence is counted only once per system organ class and once per preferred term. The number and percent of participants experiencing events are reported. Outputs reported at maximum severity show the highest severity reported by a patient per system organ class and preferred term.

All AEs will be listed.

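### Part A follow-up beyond week 25 depends on PCSK9 recovery and on AEs, but the SAP's TEAE percentages and by-visit PCSK9 means make no allowance for it

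*SAP*

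**What the plan says.** The protocol synopsis (Brief Summary) sets a common minimum: "Participants will then attend follow-up visits as outpatients for a minimum of 25 weeks as outlined in the schedule of activities". Visits then continue to a maximum whose length is redacted, unless stopping conditions are met.

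Footnote b of the Part A schedule (protocol 1.3.1) gives those conditions. Extension visits may stop "once any treatment related AEs are resolved and PCSK9 levels return to at least" a redacted percentage of baseline. A completer's last visit is the next extension visit once no AE remains open and PCSK9 has recovered; the footnote puts the second requirement this way: "after PCSK9 levels have returned to at least 80% of baseline in a blood sample collected at one of the preceding visits". That last visit repeats the early-termination assessments, "except for the collection of a blood sample for PCSK9 assessment".

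Under protocol 8.3.1, AEs are collected until the individual's participation ends, not to a fixed day.

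For the TEAE tables, SAP 5.11.1 states that "incidence and/or number of events will be reported as appropriate, by treatment group and overall". SAP 5.3 sets the denominator: "Percentages will be based on the number of participants in the column header unless otherwise specified in the footnote". SAP 5.10.1 summarises PCSK9 and ApoB, observed and change from baseline, by group and visit. Neither the SAP text nor its table list has a common AE window, a person-time rate, a summary of follow-up duration, or a rule for extension visits.

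**The concern.** PCSK9 is the marker the drug is meant to lower, and protocol 4.3.4 expects its effect to last for months. A stopping rule tied to PCSK9 makes observation time depend on dose. A rule tied to AEs makes it depend on the primary endpoint itself, because a participant with an unresolved event stays under observation and can accrue more.

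Two outputs are affected. In the TEAE and SAE tables, a column with longer follow-up has more time to collect events, and the reader has no follow-up figure with which to judge an excess over pooled placebo. In the PCSK9 tables, participants drop out of the later visits because they recovered, so the remaining mean lies below the whole cohort's. ApoB at the same visits comes from the same selected group.

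**Working it through.** **Arm sizes.** Protocol 9.5 plans about 68 Part A completers. Reading the allocation ratios as counts: 2×(6+2) + 3×(9+2) + 19 = 68, which agrees. Without Cohort 6, which was not enrolled, 49 remain: 2×6 + 3×9 = 39 active and 5×2 = 10 pooled placebo. The documents give no AE rate, follow-up time or late PCSK9 value, so everything below rests on stated assumptions.

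**TEAEs, bounding case.** Assume the same constant hazard in both arms and 50% with a TEAE by week 25. Then p(w) = 1 − 0.5^(w/25), giving 63.1%, 70.5% and 76.3% at weeks 36, 44 and 52. That is 13 to 26 points above 50%, but it keeps every active participant to week w and releases every placebo participant at week 25.

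**TEAEs with a recovery time.** Let the time T to reach 80% of baseline be lognormal, median week 30, log-SD 0.35. About 30% have recovered by week 25. Each participant leaves at the first extension visit after the one at which 80% was seen, or at the cap. Averaging p(w) over simulated participants gives these gaps in percentage points:

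| Visit spacing from week 25 | Cap (week) | Placebo leaves at week 25 | Placebo leaves at next visit |
|---|---|---|---|
| 2 weeks | 36 | 8.6 | 5.9 |
| 2 weeks | 44 | 10.7 | 8.0 |
| 2 weeks | 52 | 11.4 | 8.7 |
| 4 weeks | 36 | 10.3 | 5.0 |
| 4 weeks | 44 | 13.0 | 7.7 |
| 4 weeks | 52 | 14.0 | 8.8 |

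In the last column placebo is at 52.7% (week 27) or 55.2% (week 29). If follow-up ends at the last scheduled visit before the cap, the lowest gaps are 8.2 and 3.3. The ranges are therefore about 8 to 14 and 3 to 9 points.

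**Front-loaded events.** Put half the 25-week cumulative hazard (0.693) in the first 4 weeks. The later hazard is 0.347/21 = 0.0165 per week. The bounding case falls to 8 to 18 points, and the table's two columns to about 5 to 9 and 3 to 6.

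**PCSK9, active arm.** In the same model let PCSK9 rise linearly from 40% of baseline at week 6 to 80% at T, then on to at most 100%. With 4-week spacing, those sampled at week 36 are those with T > 32: 1 − Φ(ln(32/30)/0.35) = 43%. Their mean is 75% of baseline, against 88% for the whole cohort. Of those sampled, 29% have 32 < T ≤ 36 and so are already at or above 80%.

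A second model (60% suppression, 16-week recovery half-life, 15% within-person CV, 10% chance of an ongoing AE per visit) gives −28% at week 37 among the 34% still sampled (about 3 of 9), against −14% for all.

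**PCSK9, placebo.** In that second model 85% of placebo values are at or above 80% at week 25, so about 1 − 0.85×0.90 = 23.5% are still sampled at week 29 (simulated 23%, or 34% at 25% CV). Their mean is −7%, against +2% for the whole group. In a scenario with stronger suppression (mean −38% at week 25), the week-29 contrast with placebo is −36.8 − (−6.9) = −29.9 among those sampled and −34.1 − 2.2 = −36.3 for everyone. The placebo contrast can thus be understated.

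**The case against.** The strongest defence is that the analyses are descriptive (protocol 9.1), no safety comparison is planned (protocol 9.3.5), every AE is listed, and SAP 5.3 prints the number of observations, so thinning at late visits is visible. That limits the harm: no error rate or power is affected. It does not remove the problem, because dose columns beside pooled placebo exist to be compared, and the number of observations does not show why participants left.

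Several stronger readings are tempting and are not supported:

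- A reader might infer that late PCSK9 means contain only non-recovered participants and that recovered values are never seen. Footnote b requires a sample at or above 80% before exit; that sample is tabulated at its visit. Recovered participants with an ongoing AE also stay. Only values after exit are missing.
- A reader might infer that placebo participants all leave at once and that the artefact is 13 to 26 points. Placebo participants can stay through an AE or a chance low value, and many active participants recover early.
- A reader might carry the bias into the Part B dosing interval, which protocol 4.3.4 says "will be informed by the rate of return of PCSK9 plasma concentrations in Part A study participants". SAP sections 1 and 2 state that the study stopped after Cohort 5 and will not proceed to Part B, so that use has lapsed.

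**Conclusion.** The point stands as a reporting defect in the primary endpoint and a secondary endpoint. Follow-up after week 25 is tied by design to PCSK9 suppression and to AEs, and the SAP neither reports nor allows for it. That active arms are followed longer is an expectation, not a documented fact.

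The likely TEAE artefact is about 8 to 14 points against a 25-week placebo arm, or 3 to 9 if placebo leaves one visit later, and less if events cluster early. It rests on the assumed hazard, recovery curve, visit spacing and cap. With arms of 6 or 9 active and 10 placebo, one participant is already 10 to 17 points (1/10 to 1/6), so the artefact could not be told from chance in a single cohort, but it is systematic.

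For PCSK9, active-arm means at extension visits are enriched for slow recoverers and show more remaining suppression than the whole cohort has. Late placebo means are pulled down too, so the direction of bias in the placebo contrast is not fixed.

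**What to change.** Amend the SAP before Part A database lock, or use the post-lock addendum that SAP section 5 provides. No new data are needed.

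1. Make the lead TEAE and SAE tables run from Day 1 to the end of the minimum follow-up scheduled for everyone: the 25-week point, defined as the day in footnote b after which visits may stop. Name that day; as extracted, the schedule shows Days 43 to 169 in a late column, so defining the window by where the Monitoring Extension begins would be ambiguous. Show later events separately.
2. Report follow-up duration by arm, and whole-study TEAEs as participants with a first event per participant-year at risk. State that this does not fully correct follow-up prolonged by AEs.
3. Limit by-visit PCSK9 and ApoB means and placebo contrasts to visits scheduled for all participants. List the extension data.
4. For duration of effect, give Kaplan-Meier time to the first PCSK9 at or above 80% of baseline after having fallen below 80%, in active participants who fell below it, censored at the last sample. Without the prior-fall condition, early samples taken before suppression would count as recovery.

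Footnote b states two AE conditions, one on resolution of treatment-related AEs and one on having no ongoing AEs. They imply different follow-up lengths and must be reconciled.

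The cost is SAP wording and a few extra outputs. The small downside is that late events leave the headline table.

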### 5.11.2 Injection Site Reactions (ISR)

ISR data will be listed only.

QMD Ref: Worldwide-TMP-ST-054-1.0_Effective: 12Aug2022	Governing QMD: Worldwide-SOP-ST-026
Confidentiality Statement This document is the property of Worldwide Clinical Trials Inc. and may not be duplicated, copied, altered or removed from company without prior approval from Worldwide Quality Assurance or in compliance with Worldwide Standard Operating Procedures.	

Worldwide Clinical Trials Controlled Quality Management Document		
 WORLDWIDE CLINICAL TRIALS	Sponsor:	Eli Lilly and Company
	Protocol Number:	J4N-MC-YFAA
STATISTICAL ANALYSIS PLAN		

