**Table 2.2 Important Potential Safety Risks with LY3885125**

Potential Risk of Clinical Significance	Summary of Data/Rationale for Risk	Mitigation/Monitoring Strategy
Hypersensitivity or allergic reactions	Not specific to LY3885125. Oligonucleotide therapies, both marketed and those in development, have been associated with hypersensitivity events.	Monitor for hypersensitivity reactions in participants. Assess spontaneously reported adverse events for their likelihood to represent hypersensitivity reactions. Once identified, investigative site personnel will collect additional information to characterize the type of reaction using standardized forms. Qualified staff will have received training and have access to supportive measures to manage the reactions.
Injection-site reactions	Not specific to LY3885125. As this molecule is an injectable therapeutic, there is the potential risk of localized injection-site reactions.	Qualified staff will have received training and have access to supportive measures to manage the reactions.
CCI [REDACTED]	Specific to LY3885125. CCI [REDACTED] [REDACTED] Further information is provided in the IB.	Vital signs and ECG will be recorded across multiple scheduled time points following single and multiple doses.
CCI [REDACTED]	CCI [REDACTED] [REDACTED] CCI [REDACTED]	CCI [REDACTED] [REDACTED]

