### **8.2.7. Injection Site Reactions (ISR)**

Symptoms of a local ISR may include:

- Erythema
- Induration
- Pain
- Pruritus, and
- Edema

If an ISR is reported by a participant or investigator, the ISR Case Report Form (CRF) will be used to capture additional information about this reaction (for example, degree and area of erythema, induration, pruritus, and edema).

All positive responses of pain will require an additional assessment using the Pain Visual Analog Scale (Pain VAS). Pain measurements will be quantified using the 100-mm VAS pain score.

Management of ISRs will consist of ice packs and may include topical administration of antihistamines to alleviate itching.

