	16.2.4.1	Demographics – Full Analysis Set	IP	-
	16.2.4.2	Previous Medical History – Full Analysis Set	IP	-
	16.2.4.3	Ongoing Medical History – Full Analysis Set	IP	-
	16.2.4.4	Prior Medications – Full Analysis Set	IP	-
	16.2.4.5	Concomitant Medications – Full Analysis Set	IP	-
	16.2.5.1	Dosing Information – Safety Analysis Set	IP	-
16.2.6	PK			
	16.2.6.1	Plasma LY3885125 Concentration Listing by Subject – Safety Analysis Set	MR	-
	16.2.6.2	Urine LY3885125 Concentration, Volume, Ae, and Fe% Listing by Subject and Collection Interval – Safety Analysis Set	MR	-
	16.2.6.3	Terminal Elimination Rate for LY3885125 for Individual Subjects – PK Analysis Set	MR	-
	16.2.6.4	Plasma PK Output Text – PK Analysis Set	MR	-
	16.2.6.5	Urine PK Output Text – PK Analysis Set	MR	-
	16.2.6.6	SAS Output Text for Dose Proportionality Assessment – PK Analysis Set	MR	-
16.2.7	Safety – Adverse Events			
	16.2.7.1	Adverse Events – Safety Analysis Set	IP	-

QMD Ref: Worldwide-TMP-ST-054-1.0_Effective: 12Aug2022	Governing QMD: Worldwide-SOP-ST-026
Confidentiality Statement This document is the property of Worldwide Clinical Trials Inc. and may not be duplicated, copied, altered or removed from company without prior approval from Worldwide Quality Assurance or in compliance with Worldwide Standard Operating Procedures.	

Worldwide Clinical Trials Controlled Quality Management Document		
 WORLDWIDE CLINICAL TRIALS	Sponsor:	Eli Lilly and Company
	Protocol Number:	J4N-MC-YFAA
STATISTICAL ANALYSIS PLAN		

Section Number	Listing Number	Listing Title	Validation Method	Shell Number (if repeat)
	16.2.7.2	Injection Site Reactions – Safety analysis Set	IP	-
	16.2.7.3	Hypersensitivity Laboratory Measurements – Safety Analysis Set	IP	-
16.2.8	Safety – Labs			
	16.2.8.1	Hematology – Safety Analysis Set	IP	-
	16.2.8.2	Serum Chemistry – Safety Analysis Set	IP	16.2.8.1
	16.2.8.3	Urinalysis – Safety Analysis Set	IP	-
16.2.8	Safety – Other			
	16.2.8.6	Vital Signs Data – Safety Analysis Set	IP	-
	16.2.8.7	ECG Data – Safety Analysis Set	IP	-
	16.2.8.9	Height and Weight Data – Safety Analysis Set	IP	-
	16.2.8.10	Pharmacodynamic Data – PD Analysis Set	IP	-
	16.2.8.11	Immunogenicity Data – Immunogenicity Analysis Set	IP	-

QMD Ref: Worldwide-TMP-ST-054-1.0_Effective: 12Aug2022	Governing QMD: Worldwide-SOP-ST-026

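### Injection-site reaction CRF and pain VAS data are listed only, so no count of participants with any ISR and no summary of ISR features or VAS is planned by dose against pooled placebo

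*SAP*

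**What the plan says.** **Analysis.** SAP 5.11.2 consists of one rule: "ISR data will be listed only". SAP section 10 agrees. Its only ISR output is listing 16.2.7.2, "Injection Site Reactions – Safety analysis Set", and there is no ISR table or figure.

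**Why ISRs are collected.** The Part A primary objective is safety and tolerability after a single subcutaneous dose, with AEs and SAEs as endpoints (protocol section 3; SAP section 2). On ISRs, protocol Table 2.2 says that "there is the potential risk of localized injection-site reactions".

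**What is collected.** Under protocol 8.2.7, once a reaction is reported, "the ISR Case Report Form (CRF) will be used to capture additional information about this reaction". The examples it gives are edema, pruritus, induration and erythema, with how marked and how large they are. For pain, "Pain measurements will be quantified using the 100-mm VAS pain score". The schedule in protocol 1.3.1 makes the CRF and VAS follow from a participant's spontaneous report and sets no assessment times.

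**What the AE tables give.** SAP 5.11.1 tabulates TEAEs by system organ class and preferred term, and again with maximum severity, by treatment group. Under SAP 5.3 the groups are five doses, pooled LY3885125 and pooled placebo. The counting rule is that "Adverse event incidence is counted only once per system organ class and once per preferred term".

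**The general commitment.** Protocol 9.3.5 says that quantitative safety measurements will be summarized descriptively by treatment group and that categorical endpoints will be summarized with counts and percentages. SAP section 8 declares no change from the protocol's planned analysis.

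**The concern.** The trial anticipated this risk and built a form and a pain score to describe it, yet the plan does not summarize what they collect. A reader of the report who asks how many participants at each dose had any ISR, how marked the signs were, or how much pain was reported, compared with placebo, will find no table that answers.

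The TEAE tables answer a neighbouring question, one preferred term at a time. They carry no row for participants with any injection-site term. They also depend on each ISR having been entered as an AE, which neither document requires in so many words. Protocol 8.2.5 groups ISRs with the serious and non-serious events that the medical monitor reviews, and the general AE definition in protocol 10.3.1 would cover them. That makes coverage likely but leaves it to inference.

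**Working it through.** **1. Denominators.** The ratios in protocol 4.1.1, read as counts, reproduce the Part A total in protocol 9.5:

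- Cohorts 1-2: 2 × (6 + 2) = 16
- Cohorts 3-5: 3 × (9 + 2) = 33
- Cohort 6: 10 + 9 = 19
- Sum: 16 + 33 + 19 = 68, as stated.

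SAP section 3 says that Cohort 6 was not enrolled. That leaves:

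- LY3885125: 2 × 6 + 3 × 9 = 39, in dose groups of 6, 6, 9, 9 and 9
- Pooled placebo: 5 × 2 = 10
- Total: 49

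**2. Where each ISR data item goes.**

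| Item | Tabulated by dose and pooled placebo? |
|---|---|
| ISR entered as an AE: incidence per preferred term | Yes, SAP 5.11.1 |
| ISR entered as an AE: maximum AE severity per preferred term | Yes, SAP 5.11.1 |
| Participants with at least one ISR of any kind | No |
| CRF features (degree and area of each sign) | No, listed only |
| Pain VAS | No, listed only |

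AE severity does not stand in for the CRF features. Protocol 10.3.4 grades intensity by interference with daily activities and need for treatment, not by the extent of a local sign.

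**3. What preferred-term rows can reveal.** Participants are counted once per term. The number with any ISR therefore lies between the largest injection-site row and the sum of those rows, and the table cannot say where.

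- If one participant has three terms, that participant appears in all three rows. No row is reduced, but adding the rows overcounts.
- If different participants have different terms, each row understates the total.

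The system organ class row does not settle it, because it counts every term in the class and not just the injection-site ones.

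**4. Illustration with assumed data.** Suppose 3 of 9 participants at one dose each have one ISR, coded to three different terms. With exact (Clopper-Pearson) 95% limits, lower = Beta(0.025; x, n − x + 1) and upper = Beta(0.975; x + 1, n − x):

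- As planned: three rows of 1/9 = 11.1% (0.3% to 48.2%)
- Combined row: 3/9 = 33.3% (7.5% to 70.1%)

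From the three rows alone, the number affected could be 1, 2 or 3. A second assumed case: 8 of 39 LY3885125 participants (20.5%) have an ISR, one term each, over five terms. The largest pooled row could then be as small as 2/39 (5.1%), since 2 + 2 + 2 + 1 + 1 = 8.

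**5. Limits of any ISR table here.** With no ISR observed, the upper exact 95% limits are 45.9% for 0/6, 33.6% for 0/9, 30.8% for 0/10 and 9.0% for 0/39. The table would describe. It would not establish a dose trend or a difference from placebo, and protocol 9.3.5 plans no statistical comparison of safety endpoints.

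**The case against.** The case for leaving the plan alone has substance.

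- **AE tables already exist.** A reader might infer from SAP 5.11.2 that no ISR incidence or severity by dose against placebo will be reported at all. The documents do not support that. ISRs entered as AEs get both, per preferred term, with pooled placebo alongside. This stands, and it limits the point to the three untabulated items.
- **Fragmentation may be small.** Protocol 10.3.4 asks sites to record the diagnosis rather than separate signs whenever possible. If followed, one reaction yields one term. This stands in part. The instruction is qualified, and where it is followed the sign-level detail exists only on the CRF, which is never summarized.
- **The data are sparse and selective.** The CRF is triggered by spontaneous report and the VAS by reported pain. With about 49 participants and listings sorted by treatment group, a hand count is feasible. Protocol 9.3.5 also allows further analysis if the data warrant it. All true, but a hand count has no prespecified rule for what counts as an ISR or for combining CRF and AE sources.
- **ISRs have no special rank.** A reader might take them to be the trial's principal tolerability measure. The protocol does not say so: the primary endpoints are AEs and SAEs, no AEs of special interest are defined (8.3.3), and Table 2.2 describes ISRs as not specific to this compound.
- **Split injections.** A reader might infer that higher doses needed several injections and that this obscures any dose trend. The volumes and doses are redacted, so it cannot be shown that any cohort was affected.

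**Conclusion.** The point holds as a modest reporting gap. The plan produces no combined count of participants with any ISR, no summary of ISR CRF features and no VAS summary by dose against pooled placebo. ISRs reach tables only as separate AE preferred terms, and only to the extent that CRF entries were also recorded as AEs.

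The rule also sits badly with protocol 9.3.5 and with the no-changes statement in SAP section 8. That is tension rather than flat contradiction: the examples that 9.3.5 gives for quantitative data are laboratory tests, vital signs and ECGs, so applying it to the VAS and CRF signs is a natural reading and not an explicit instruction.

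No sample size, error rate or formal comparison is affected. The sizes of 39 and 10 assume that the allocation ratios are the group counts. The 3 of 9 and 8 of 39 cases are assumed, and show what the planned tables could conceal, not what occurred.

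**What to change.** Keep listing 16.2.7.2. Reword SAP 5.11.2 and add one descriptive table to SAP section 10, on the Safety Analysis Set, with the SAP 5.3 columns (each dose, pooled LY3885125, pooled placebo):

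- n and % of participants with at least one ISR, defined as an ISR CRF entry or any injection-site preferred term, each participant counted once;
- n and % with each sign, and its maximum recorded degree where the CRF records one;
- maximum pain VAS among participants reporting pain, with their number shown, since this subgroup is selected by reporting.

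State in SAP 5.11.2 whether every ISR CRF entry is also an AE record. If it is not, say so in a footnote to the TEAE tables.

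The cost is a wording change and one small table from data already collected. The downside is an extra table that may be nearly empty and rests on spontaneous reports, so it should carry a note to that effect. SAP section 5 allows the change by amendment before Part A database lock and by a post-lock addendum afterwards.
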